**Table 2. Message sets for formative message testing in a 2x3 between subjects experiment (Aim 1 Phase 2)**

		THREAT	
		ABSOLUTE RISK (AR)	RELATIVE RISK (RR)
EFFICACY	Quit only (Q)	Set 1: AR/Q (n = 8)	Set 2: RR/Q (n = 8)
	Switch only (S)	Set 3: AR/S (n = 8)	Set 4: RR/S (n = 8)
	Combined quit + switch (QS)	Set 4: AR/QS (n = 8)	Set 6: RR/QS (n = 8)

**Aim 1, Phase 1: Study 2 –ONLINE RATING SURVEY:** In Phase 1, Study 2 we will conduct an online survey to quantitatively examine young adults’ perceptions of 8 absolute risk and 8 relative risk anti-tobacco messages and quit/switch efficacy statements. To reduce participant burden, each participant will view a random sample of messages as follows: n = 5 absolute and relative risk anti-tobacco messages (of N = 24), and n = 3 (of N = 12) efficacy messages. They will be asked to rate absolute and relative risk antitobacco messages and quit/switch efficacy statements for perceived message effectiveness, likeability, and reactance.

**Aim 1, Phase 1: Study 3 –IN-DEPTH INTERVIEWS:** Interviewees will be asked to share their reactions to the 24 textual anti-tobacco messages tested in Study 2. Specifically, interviewees will be asked to rate their top 5 (of N =12) absolute risk and top 5 (of N =12) relative risk antitobacco messages. We will then qualitatively explore their rationale for their top 5 selected messages.

**Aim 1, Phase 2: ONLINE FACTORIAL EXPERIMENT** (NCT05393869): Using a 2x3 factorial experiment (Table 2), plus control group design we will test the influence of AR and RR message framing on perceived effectiveness, tobacco risk perceptions, and behavioral intentions in young adult ever polytobacco users. Participants will be randomized to one of 8 conditions, including 6 experimental sets of AR and RR anti-tobacco messages (Table 3) and a control set of AR or RR regulatory control messages. We will present 8 messages within each experimental and control set. An expert panel of scientists, selected and invited by the mentoring team, will review all messages, which we will further refine based on expert feedback prior to testing in Aim 1, Phase 2 (NCT05393869).

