#### **B. Aim 1, Phase 1: Study 2—ONLINE RATING SURVEY Procedures**

**Prescreening and consent.** Participants will be recruited via Prolific, an online platform open to participants who are compensated for completing surveys and online behavioral experiments. Prolific is an efficient online recruitment platform, ideal for pilot studies, as it can deliver a high number of participants, per day, at low cost (recommended, minimum \$0.175 per minute of survey participation time). Data quality provided by Prolific

samples is high and comparable to that from traditional college student samples. Prolific offers access to over 38,000 United States nationals. Prolific samples are young; approximately 1/3 of the Prolific population reports ages < 35 years old, which makes Prolific an ideal pool for recruiting young adult survey participants. Prolific is also a viable method for recruiting hard-to-reach populations for survey research, including LGBT populations.

Prescreening will be conducted via Prolific. Prolific is able to segment our population of interest for age (18-35 years) and currently residing the United States. It can also help us track gender and sexual orientation in order to balance recruitment. We are able to add in a custom pre-screening question to assess for prior history of ever nicotine or tobacco use (i.e., use of combustible tobacco or e-cigarette products at least once).

Participants who meet eligibility criteria will be directed to an online survey administered via Qualtrics. Consent will be completed online prior to the Qualtrics survey.

Qualtrics survey procedures. Following online consent, participants will be directed to complete a survey that includes questions assessing tobacco use, including exposure to tobacco related advertising, coupons, and discounts; harms perceptions and tobacco-related behavioral intentions (i.e., quit, switch). It is estimated that the survey will take 20 minutes to complete.

Participants will answer baseline survey questions before viewing a random sample of 5 messages (of N = 24); they will rate each message for perceived effectiveness, likeability, and reactance. After viewing all messages, participants will complete a post-survey and receive \$0.175/minute (estimated \$3.50) via Prolific for participating.

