### **B. Aim 1, Phase 1: Study 2-ONLINE RATING SURVEY Data Analysis**

For online rating survey data, we will describe mean and median values of participants' ratings of perceived message effectiveness, likeability, and reactance.

In exploratory analyses, we will assess whether there are systematic differences in participants' ratings by message type (AR vs RR), gender, LGBT status (vs non-LGBT), race/ethnicity, age (e.g., 18-24 vs 25-35) and tobacco user type (e.g., current, former, never polytobacco user). We will test mean differences between groups using t-tests or ANOVA. If there are violations of assumptions (e.g., normality) we will test median differences between groups using Wilcoxon rank-sum test (two groups) or Kruskal Wallis test (more than 2 groups).

We will also run exploratory regression models to evaluate the effect of risk message type (e.g., absolute risk vs. relative risk) and efficacy message type (e.g., quit; switch; combination) on messages on perceived message effectiveness, likeability, and reactance; controlling for pro- and anti-tobacco marketing exposure, baseline risk and efficacy perceptions and behavioral intentions. For models testing the effect of efficacy

messages, we will conduct overall F-tests to determine if there is an effect of efficacy message type in each model. If so, pairwise t-tests will be conducted, and Holm's procedure will be used to control Type I error rate.

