Sample Size Justification: For Aim 1, Phase 1, Study 2—ONLINE RATING SURVEY: An analytic sample size of 200 participants per group will allow us to detect differences between two groups in terms of perceived message effectiveness. Assuming a pooled standard deviation of 1.0 units, the study would require a minimum sample size of  $n = 199$  for each group to achieve power of 80% and two-sided significance level of  $p = .05$  for detecting a 0.25 unit difference in perceived message effectiveness scores, which has been reported previously in the literature. Under these same parameters, we will be able to detect a 0.25 unit difference in PME scores with 75% probability assuming a significance level of  $p = 0.1$ . As multi-group comparisons are exploratory, we believe this a prior sample size calculation is appropriate. As our desired analytic sample size is  $N = 500$  participants ( $n = 250$  participants per experimental group; AR vs RR messages); we have inflated our overall sample size is inflated by 10% to account for estimated inconsistencies between prescreening and survey responses, resulting in an overall sample size of  $N = 550$ .

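### Study 2 power statement is wrong as written: 199 per group gives 70% power, not 80%, at two-sided 0.05, and its separate AR and RR groups conflict with the rating procedure

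*Combined protocol and SAP*

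**What the plan says.** The Sample Size Justification in Section VI.B opens with 200 participants per group. Assuming a pooled SD of 1.0 and a 0.25-unit difference in perceived message effectiveness, it asks for a "minimum sample size of $n = 199$ for each group to achieve power of 80% and two-sided significance level of $p = .05". It adds that, with the same parameters, "we will be able to detect a 0.25 unit difference in PME scores with 75% probability assuming a significance level of" 0.1. It closes with an analytic total of 500, made up of 250 "participants per experimental group; AR vs RR messages", inflated by 10% to 550.

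The procedure is described differently. In Section III.B, the Study 2 paragraph under Table 2 says "each participant will view a random sample of messages as follows: n = 5 absolute and relative risk anti-tobacco messages (of N = 24"; Section IV.B says "Participants will answer baseline survey questions before viewing a random sample of 5 messages (of N = 24". The same Section III.B paragraph describes the material as "perceptions of 8 absolute risk and 8 relative risk anti-tobacco messages and quit/switch efficacy statements", so the pool is given both as 8 + 8 and as 24.

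The analysis text in Section VI.B leads with descriptive means and medians. It labels the AR versus RR comparison exploratory and says "We will test mean differences between groups using t-tests or ANOVA", with rank-based tests as the fallback. It also plans exploratory regressions on message type.

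**The concern.** There are two problems.

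First, the two power sentences cannot both be true. With n, difference and SD fixed, moving alpha from 0.05 to 0.1 must raise power, yet the text goes from 80% down to 75%. The first sentence is also wrong by itself, because 199 is too few for 80% power at two-sided 0.05.

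Second, the calculation treats AR and RR as two separate sets of people. The survey procedures do not assign anyone to AR only or RR only; each participant rates a mixed sample. None of the quoted figures is then the power of the AR versus RR comparison as the survey would run it, and a test for two independent groups does not match the data.

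At stake is the accuracy of the stated power and the choice of test for an exploratory comparison. The adequacy of N = 500 is not put in doubt.

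**Working it through.** **Inputs, all from the Section VI.B justification:** difference 0.25; SD 1.0; two-sided alpha 0.05; power 80%; group sizes 199, 200 and 250; second statement 75% at alpha 0.1.

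**1. Trying to reproduce 199.** By normal approximation, n per group = 2(z_alpha + z_power)² × (SD/difference)².

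- Two-sided 0.05, 80% power: 2 × (1.960 + 0.842)² / 0.0625 = 251.2, so 252. The noncentral t gives 252.1, so 253.
- Two-sided 0.10, 80% power: 2 × (1.645 + 0.842)² / 0.0625 = 197.8, so 198. The noncentral t gives 198.5, so 199.

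The figure 199 does not follow from the stated inputs. By the t calculation it is the answer for two-sided 0.10 at 80% power. One-sided 0.05 at 80%, and two-sided 0.05 at 70%, also give 199. A Wilcoxon adjustment (264) and a one-sample or paired t-test (128) do not.

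**2. Power at the group sizes named.** Noncentrality = 0.25 × √(n/2). At n = 199 it is 2.494, so approximate power at two-sided 0.05 is Φ(2.494 − 1.960) = 0.703. The exact noncentral-t values are:

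| n per group | two-sided 0.05 | two-sided 0.10 |
|---|---|---|
| 199 | 70.1% | 80.1% |
| 200 | 70.3% | 80.3% |
| 250 | 79.7% | 87.4% |

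No group size named in the paragraph gives 75% at 0.10. By normal approximation that would need 173 per group.

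**3. Detectable difference** with 80% power at two-sided 0.05: 0.28 at 199 or 200 per group, and 0.25 at 250.

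**4. Who sees both types.** The plan does not say how the 5 messages are drawn. Assume a simple random draw from a pool with equal numbers of each type:

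- 12 AR + 12 RR: 1 − 2·C(12,5)/C(24,5) = 1 − 1,584/42,504 = 96.3%.
- 8 AR + 8 RR: 1 − 2·C(8,5)/C(16,5) = 1 − 112/4,368 = 97.4%.

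**5. Effect of treating all ratings as independent.** Let m be the number of AR messages among a participant's 5, and r the within-person correlation of ratings. The plan gives no r, so 0.3 to 0.7 is assumed. With messages as fixed, true variance / naive variance for AR versus RR = [r·E(2m − 5)² + 5(1 − r)]/5, where E(2m − 5)² is 4.13 for 12 + 12 and 3.67 for 8 + 8.

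- 12 + 12: 0.95 at r = 0.3, 0.88 at r = 0.7.
- 8 + 8: 0.92 at r = 0.3, 0.81 at r = 0.7.

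Analysing pooled ratings as independent would therefore be mildly conservative for this contrast.

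**The case against.** The strongest reply is that little depends on these sentences. The planned 250 per group meets the 80% target almost exactly, the lead analysis is descriptive, the group comparisons are exploratory, and Section III.B.1 already cites a phase 1 result, so the survey may be complete. If the procedure text governs, AR versus RR would rest on about 500 × 2.5 = 1,250 ratings per type. With an assumed rating-level SD of 1.0 and the variance ratios above, power for a 0.25 difference would then exceed 99.9%. All of this stands as a limit on the consequences. It does not make either power sentence true.

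Three narrower points also have force. The source of 199 cannot be identified, since several input errors lead to it. The 96% to 97% figures depend on a simple random draw that the plan does not state. The text says t-tests without specifying independent samples, and the regressions might have been meant to handle repeated ratings, although nothing says so.

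The reply leaves the design conflict unresolved. Section III.B.2 mentions randomly assigned messages, but that does not create AR-only and RR-only groups. The need to account for the participant also extends beyond AR versus RR. If ratings are pooled for comparisons such as gender or user type, the design effect would be 1 + 4r, or 2.2 to 3.8 for r = 0.3 to 0.7.

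**Conclusion.** The concern holds; both power sentences are wrong as written. At two-sided 0.05, 199 per group is 54 short of the 253 needed and gives 70.1% power, about 10 points below the stated 80%. The 75% figure at 0.1 should be about 80% (199 or 200 per group) or 87% (250 per group). These results use only the plan's own inputs.

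The AR and RR grouping in the justification also contradicts the rating procedure in Sections III.B and IV.B. That nearly all participants would rate both types assumes a simple random draw, and holds for either pool size. Power for the within-participant comparison cannot be derived from the documents, because no within-person correlation is given.

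The error lies in the justification and in the match between test and design. It should be corrected, but it does not show that N = 500 is inadequate.

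**What to change.** - Restate the first sentence: at two-sided 0.05, 253 per group are needed for 80% power to detect 0.25 with SD 1.0; 199 to 200 per group gives about 70%, and the planned 250 about 80%.
- Delete the 75% sentence, or correct it to 80% at 199 to 200 and 87% at 250 per group for two-sided 0.10.
- Reconcile the 250-per-group AR versus RR wording with Sections III.B and IV.B, and state whether the pool is 8 + 8 or 24 and how the 5 messages are drawn.
- If the procedure stands, treat AR versus RR as a within-participant factor. Use a method that accounts for the participant, for example a random participant intercept, in place of an independent two-sample t-test or rank-sum test. Whether to add a random message effect depends on whether inference is meant to reach beyond these messages, and is for the sponsor to decide.

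The cost is two sentences, a reconciled description and one line on the model. N = 500 and enrolment are unchanged. If Study 2 is complete, the correction applies to analysis and reporting only. The quoted power at 199 to 200 per group becomes less favourable.

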#### **C. Aim 1, Phase 1: Study 3—IN-DEPTH INTERVIEWS:**

For in-depth interviews the goal will be to refine messages and determine which images should be matched to the AR and RR anti-tobacco messages. These images will then move on to Aim 1 Phase 2 of this study. We will qualitatively summarize the feedback in response to each focus group question using rigorous and accelerated data reduction (RADaR) analytic methods. Used in applied research, RADaR organizes transcribed textual data from qualitative interviews into data tables; which are then organized and iteratively reduced, coded, and analyzed using team-based coding.

Sample size justification: For Aim 1, Phase 1: Study 3—IN-DEPTH INTERVIEWS our planned analytic sample size of  $N = 8$  is designed to maximize the information power of qualitative research in which an initial sample of 6- 8 participants for is recommended for qualitative interviews. The aim of these interviews is to test existing messages to improve any communication issues. If we do not reach thematic saturation, we will enroll additional participants up to a maximum of  $N = 16$ . We have inflated the overall sample size to 20 participants to allow for ~20% dropout.

#### **D. Aim 1, Phase 2: ONLINE FACTORIAL EXPERIMENT (NCT05393869) Data Analysis**

We will fit linear regression models to evaluate the effect of condition on perceived effectiveness, risk perceptions, and behavioral intentions. Covariates will include exposure to pro- and anti-tobacco marketing, and baseline risk perception and behavioral intention items (per respective models). Baseline and post-viewing scores may be transformed if violations of assumptions are detected. We will conduct overall F-tests to determine if there is an effect of condition in each model. If so, pairwise t-tests will be conducted, and Holm's procedure will be used to control Type I error rate. Exploratory analyses will be conducted to determine if there is an interactive effect between Condition x Topic. *Responses will be examined by gender and sexual orientation to determine if there are systematic differences.*

Sample Size Justification: For the Aim 1, Phase 2: ONLINE FACTORIAL EXPERIMENT

(NCT05393869) an analytic sample size of 400 participants per group will allow us to detect the best message in terms of risk perception score with 75% probability assuming the mean score in the best group is at least 0.1 standard deviations better than the mean score in the second best group. As effect sizes of 2 or greater are reported in the literature for this outcome, we do not consider smaller differences to be of interest. As our analytic sample size is N = 2800 participants (n = 400 participants per experimental or control group); we have inflated our overall sample size is inflated by 5% to account for estimated inconsistencies between prescreening and survey responses, resulting in an overall sample size of N = 2940.

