For Aim 1, Phase 2-ONLINE FACTORIAL EXPERIMENT (NCT05393869): Primary outcome measures are presented in **Table 1**. These measures were largely selected from the Tobacco Regulatory Research PhenX Toolkit. Baseline questionnaires will assess ENDS and combustible tobacco use, pro- and anti-tobacco advertising exposure, receptivity, social media use, risk perceptions, self- and response efficacy, and behavioral intentions. Post-viewing their assigned message condition, all participants will be asked about their responses to the posts including perceived acceptability, attitude toward, and effectiveness of the messages. All baseline measures (excluding social media use and prior anti-tobacco message exposure) will be asked post-viewing all messages. Finally, sociodemographic questions also include age, race/ethnicity, education level, location (state, county, rurality), sexual orientation and gender identity.

***The purpose of the R00 Phase*** is to identify which anti-polytobacco messages most strongly influence LGBT YA's attention, tobacco risk perceptions, and behavioral intentions (Aim 2: NCT05972941) and evaluate the impact of exposure to anti-polytobacco communications delivered by mobile multimedia messaging (MMS) on tobacco use over time in YA polytobacco users of diverse sexual orientations and gender identities (Aim 3: (NCT06644664))

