## C.2 Measurement / Instrumentation

For Aim 2 focus groups, a focus group guide will be developed and will be used to facilitate the research for preliminary work. Focus groups: Via semi-structured interview, we will ask participants about polytobacco use patterns, risk perceptions, and responses to CT messages.

For the Aim 2 eye-tracking experiment (NCT05972941), outcomes of interest are as follows:

Primary;	Attention	During exposure	Visual attention measured by eye-tracking on areas of interest (text, graphic): first fixation, dwell time (milliseconds), heat map
Primary;	Perceived effectiveness	Post-exposure to each message	Includes general perceived effectiveness (e.g., "The messages I received messages were worth remembering") and health-specific perceived effectiveness ("The messages I received made me concerned about the health effects of polytobacco use")
	EPPM Construct		Psychological reactance
Primary;	Risk Perceptions	Pre- and post-test	We will ask participants to report the significance, severity, and seriousness of health threats from tobacco use, absolute/relative risks of polytobacco use (and vs exclusive ENDS use)
Primary;	Behavioral Intentions	Pre- and post-test	Behavioral intentions to use tobacco; intentions quit all tobacco, intentions to switch to exclusive ENDS use
Secondary;	EPPM Constructs	Pre- and post-test	Self-efficacy to quit tobacco, response efficacy

For the 1-week follow-up a survey will be developed. Questions will quantitatively assess recent tobacco and ENDS use and health risk perceptions. Message recall will be assessed using quantitative and qualitative survey items.

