#### **D. Aim 1, Phase 2: ONLINE FACTORIAL EXPERIMENT (NCT05393869) Procedures**

Prescreening and consent. Participants will be recruited via Prolific, an online platform open to participants who are compensated for completing surveys and online behavioral experiments. Prolific is an efficient online recruitment platform, ideal for pilot studies, as it can deliver a high number of participants, per day, at low cost (recommended, minimum \$0.175 per minute of survey participation time). Data quality provided by Prolific samples is high and comparable to that from traditional college student samples . Prolific offers access to over 38,000 United States nationals. Prolific samples are young; approximately 1/3 of the Prolific population reports ages < 35 years old, which makes Prolific an ideal pool for recruiting young adult survey participants. Prolific is also a viable method for recruiting hard-to-reach populations for survey research, including LGBT populations .

Prescreening will be conducted via Prolific. Prolific is able to segment our population of interest for age (18-35 years) and currently residing the United States. It can also help us track gender and sexual orientation in order to balance recruitment. We are able to add in a custom pre-screening question to assess for prior history of ever nicotine and tobacco use.

Participants who meet eligibility criteria will be directed to an online survey administered via Qualtrics. Consent will be completed online prior to the Qualtrics survey.

Qualtrics survey procedures. Following online consent, participants will be directed to complete a survey that includes questions assessing tobacco use, including exposure to tobacco related advertising, coupons, and discounts; harms perceptions and tobacco-related behavioral intentions (i.e., quit, switch); and online/social media use questions.

Participants will answer baseline survey questions before random assignment to 1 of 6 experimental conditions in the 2 (Threat: Absolute/Relative Risk) X 3 (Efficacy: Quit, Switch, Quit plus Switch) design. Participants will view 8 randomly-ordered, anti-tobacco messages within their assigned condition; they will rate each message for perceived effectiveness and reactance. After viewing all messages, participants will complete a post-survey and receive \$0.225/minute (estimated \$4.50) via Prolific for participating.

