Consented participants will be directed to the online survey. At the beginning of the survey, we will ask participants to confirm that they are taking the survey in a well-lit area and that their face and eyes are clearly viewable on their webcam. We will include example images of good vs. poor lighting. If participants respond, "I am using a desktop computer or laptop. I am in an area that is well lit, and I can see my face and eyes clearly," then they will be directed to the survey. If they respond, "I have a desktop computer or laptop, but I am currently in an area that is not well lit and I cannot see my face or eyes clearly on my webcam. Please email me a link to the survey, and I will complete the iMotions task when I am in an area with better lighting," then research staff will then email these participants a direct link to the survey that they can take at a convenient time. We will send up to 9 survey reminders via email, phone call or text.

Once the survey begins, participants will complete baseline questionnaires before proceeding to the remote eye-tracking experiment. At this point, participants will be randomly assigned to 1 of 2 experimental conditions (CT or NT messages). iMotions provides an online platform for remote eye-tracking data collection using a webcam connected to a desktop or laptop computer to track eye movements during the study. Participants will be informed that their webcam needs to be turned on during the study. Prior to viewing images, calibration procedures will be conducted to assure data quality; if participants cannot be calibrated, participation will end. Participants will view a series of randomized messages (8 messages, for 10 seconds each, within assigned conditions. A 10 second viewing time is greater than needed (6 seconds) to assess visual attention.

Message versions will include similar messaging and imagery but different layouts to mitigate viewing bias, as we anticipate that a majority of participants will tend to read left to right and top to bottom. After each message, participants will report perceived effectiveness and reactance. To re-center eyes, participants will view an "X" centered on-screen for 10 seconds. Post eye-tracking, participants will complete demographic and contextual questions prior to exiting the survey. Participation is expected to last 20 minutes. Participants will receive a \$50 gift card.

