**F. Aim 2 Eye-tracking (NCT0597294) Data Analysis**

*Hypothesis: Psychophysiological data will indicate that culturally targeted messages attract greater attention.*

Anti-polytobacco messages will be divided into text and graphic AOIs. Dwell time on the textual message (in milliseconds) is the primary eye-tracking outcome. We will use linear regression models to compare message type (CT vs NT) and framing (RR vs AR) on average dwell time and proportion of time viewing AOIs.

*Hypothesis: Exposure to targeted messages will result in greater perceived effectiveness of anti-polytobacco messages.*

Generalized linear models (GLMs) will be fit to examine differences in perceived effectiveness by message type (CT vs NT). Covariates will include baseline measures in applicable models and prior exposure tobacco communications. We will also investigate gender differences. Exploratory analyses: We will conduct exploratory analyses on secondary outcomes of interest. Specifically, we will fit generalized linear models (GLMs) to examine differences in EPPM constructs, risk perceptions, behavioral intentions, and 1-week recall by message type (CT vs NT).

Sample size justification: Virtual lab study. Differences in dwell time from eye-tracking antitobacco communications studies (PI: [name]) provide the basis for estimates. Assuming a 1.1 second standard deviation, 108 participants (n = 54 per arm) will provide a 95% chance of detecting an 0.6 second mean difference in dwell time on AOIs, at 80% power. Data from our prior tobacco warning studies indicate up to a 0.8 second difference in dwell time between conditions ([name], unpublished). A 0.6 second difference in dwell time is scientifically important as the brain can register stimuli within 0.03 seconds per fMRI. The enrollment number of n=300 will account for any duplicate responses, high abandonment rate for the I-motions portion of the survey after consent has been completed, and any low-quality eye tracking data recorded due to remote I-motions software.

*Research question: How does culturally targeting influence message recall?*

For quantitative survey responses, generalized linear models (GLMs) will be fit to examine differences in message recall by message type (CT vs NT). Covariates will include baseline measures in applicable models and prior exposure tobacco communications. We will also investigate gender differences.

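### Perceived-effectiveness models appear to omit the baseline risk perceptions and intentions that both trials collect, at a modest and avoidable cost in precision

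*Combined protocol and SAP*

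**What the plan says.** **Aim 1 Phase 2.** Section VI.D names three modelled outcomes: "We will fit linear regression models to evaluate the effect of condition on perceived effectiveness, risk perceptions, and behavioral intentions". The next sentence gives the covariates: "Covariates will include exposure to pro- and anti-tobacco marketing, and baseline risk perception and behavioral intention items (per respective models".

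**Aim 2.** Section VI.F sets up generalized linear models for perceived effectiveness by message type and then says "Covariates will include baseline measures in applicable models and prior exposure tobacco communications". The same sentence appears again in VI.F for message recall.

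**When perceived effectiveness is measured.** It is measured only after exposure. For Phase 2, IV.D says of the messages in the assigned condition that "they will rate each message for perceived effectiveness". For Aim 2, IV.F says "After each message, participants will report perceived effectiveness and reactance", and the outcome table in III.C.2 gives the timing as "Post-exposure to each message" and labels the outcome primary.

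**What is collected beforehand.** In Phase 2 the baseline questionnaire in III.B.2 covers risk perceptions, self- and response efficacy, and intentions, and "All baseline measures (excluding social media use and prior anti-tobacco message exposure) will be asked post-viewing all messages". In Aim 2 the table in III.C.2 marks risk perceptions and intentions as measured both before and after exposure. IV.F confirms that "participants will complete baseline questionnaires before proceeding to the remote eye-tracking experiment", with random assignment at that point.

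**The Phase 1 rating survey.** The exploratory regressions in VI.B model perceived message effectiveness and control for marketing exposure together with baseline risk perceptions, efficacy perceptions and intentions. No qualifier restricts which baseline item goes with which outcome.

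**The concern.** The qualifiers in VI.D and VI.F most naturally mean that each outcome is adjusted for its own pre-exposure score. Perceived effectiveness has none, so nothing but prior exposure to marketing or tobacco communications is left in its model. Yet how harmful a person already thinks tobacco is, and what they already intend to do about it, could well predict how they rate an anti-tobacco message. The plan's conceptual model (section II) puts perceived threat and efficacy at the centre of message response, and VI.B uses these items as covariates for the same outcome.

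What is at stake is precision. It matters more in Aim 2, where the planned 54 per arm was sized on dwell time and perceived effectiveness has no sample-size basis of its own. There is a second cost: if the authors did intend a wider covariate set, the text does not say so, and the set for a primary outcome stays open until someone chooses it.

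**Working it through.** **1. The plan's own figures.** Neither concerns perceived effectiveness, but both come out close to what is stated.

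- Aim 2 (VI.F): SD 1.1 s, difference 0.6 s, 80% power. I read the stated 95% chance as a two-sided 5% level. The normal formula gives n = 2 × (1.960 + 0.842)² × (1.1/0.6)² = 52.8, so 53 per arm. The t-test gives 53.7, so 54, with power 0.802. The stated 54 is reproduced.
- Phase 2 (VI.D): the probability of selecting the best group with 400 per group and a 0.1 SD lead is 0.733 for seven groups and 0.759 for six, against the stated 75%.

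No covariates enter either calculation, so this point changes no stated number.

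**2. The covariate texts side by side.**

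| Section | Outcome includes perceived effectiveness? | Prior exposure | Baseline risk perceptions and intentions |
|---|---|---|---|
| VI.B, Phase 1 survey | Yes | Yes | Yes, unrestricted |
| VI.D, Phase 2 | Yes | Yes | Named, but limited to respective models |
| VI.F, Aim 2 | Yes | Yes | Baseline measures, not itemised, in applicable models |

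**3. What adjustment could gain.** Let *r* be the multiple correlation that the baseline items add beyond the covariates already in the model. The documents give no value, so 0.1 to 0.5 is an assumption. The standard error is multiplied by √(1 − r²), and the equivalent sample size is n/(1 − r²). With a two-sided 5% t-test and no added covariate, the difference detectable with 80% power is 0.544 SD at 54 per arm and 0.198 SD at 400 per group (one pairwise contrast, before any Holm adjustment). Multiplying by the factor gives:

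| r | SE factor | SE reduction | Aim 2 detectable difference (SD) | Aim 2 equivalent n per arm | Aim 2 power at 0.5 SD | Phase 2 detectable difference (SD) |
|---|---|---|---|---|---|---|
| 0 | 1.000 | 0 | 0.544 | 54 | 0.731 | 0.198 |
| 0.1 | 0.995 | 0.5% | 0.541 | 54.5 | 0.735 | 0.197 |
| 0.2 | 0.980 | 2.0% | 0.533 | 56.2 | 0.748 | 0.194 |
| 0.3 | 0.954 | 4.6% | 0.519 | 59.3 | 0.770 | 0.189 |
| 0.4 | 0.917 | 8.3% | 0.499 | 64.3 | 0.802 | 0.182 |
| 0.5 | 0.866 | 13.4% | 0.471 | 72.0 | 0.844 | 0.172 |

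The 0.5 SD target is for illustration only; the documents set no perceived-effectiveness effect for Aim 2. The only such difference they cite is 0.25 units with SD 1.0 (VI.B, a different contrast). At 0.25 SD and 54 per arm, power is 0.251 unadjusted and 0.318 at r = 0.5, so adjustment helps but does not rescue an effect of that size.

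**4. What adjustment costs.** Two arms of 54 leave 108 − 2 = 106 error degrees of freedom. A few baseline scores use up a few of these, which is negligible.

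**The case against.** The strongest reply is that the exclusion is inferred. Neither section says that perceived-effectiveness models omit risk perceptions or intentions. VI.D names those items in the sentence straight after listing perceived effectiveness as an outcome. In VI.F the same covariate sentence is applied to message recall, which cannot have a pre-exposure score either. If it meant only an outcome's own baseline, its reference to baseline measures would be empty there. VI.B shows that the authors already think of these items as covariates for this outcome. This stands as a limit on certainty, most of all for Aim 2. It does not remove the point, because under either reading the text does not fix the covariate set, and the same sentence would settle it.

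A reader might also infer that these models contain no prognostic baseline covariate at all. The documents do not support that. Prior marketing or communication exposure is in both models, and whether it is prognostic cannot be judged from the text.

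It is also fair to say that the gain is assumed and may be negligible, that 400 per group makes it less pressing in Phase 2, and that enrolment of up to 300 in Aim 2 could leave more than 108 usable ratings. All of this stands. The percentage fall in the standard error does not depend on sample size, however.

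Finally, half the Phase 2 sample are nonusers (III.B.1), for whom intentions to quit or to switch may not apply. Requiring those items in every model could create structural missingness. This stands, and it narrows the fix.

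**Conclusion.** The point holds as one of efficiency and specification. On the natural reading of VI.D, and a likely but less certain reading of VI.F, perceived effectiveness is adjusted only for prior exposure, although baseline risk perceptions and intentions are in hand and VI.B uses them for the same outcome.

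The size rests wholly on the assumed added correlation. From r = 0.1 to 0.5 the gain runs from practically nothing to a standard error about 13% smaller, which in Aim 2 is like having between 54.5 and 72 per arm in place of 54.

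It would go too far to infer that the treatment comparison is biased or its Type I error inflated: assignment is random, so the unadjusted comparison remains valid. Nor do the documents show that a known amount of precision is lost, or give a reason to add both baseline scores to the risk-perception and intention models, which already have baselines of their own.

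**What to change.** Add one sentence to each of VI.D and VI.F, fixed before data are seen:

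- **VI.F (Aim 2):** *The perceived-effectiveness model will adjust for prior exposure to tobacco communications, baseline risk perceptions and baseline behavioral intentions.* Name the scores. Eligibility admits people who currently use only ENDS, so check that any switching item used applies to them.
- **VI.D (Phase 2):** the same, with prior pro- and anti-tobacco marketing exposure. Restrict the intention covariate to items that apply to all participants, users and nonusers alike, such as intentions to use tobacco.

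VI.B also adjusts for baseline efficacy perceptions. The two sections should say whether these are in or out, with the same check on applicability to nonusers. The models for risk perceptions and intentions need no change on this account.

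The cost is two sentences and a few degrees of freedom. No new data are needed, and the stated sample sizes stay as they are.
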